12.0 Data Analysis

The Sponsor will judge the clinical and statistical significance of the study based on a comparison of observer-blind data collected at baseline and the primary endpoint using the primary outcome measure, which is the CAPS. Descriptive statistics will be computed overall and within the three dose conditions for all available data from outcome measures, including minimum, maximum, average, and standard deviation. Distributional characteristics will be examined for outliers and extreme values and, if either is evident, nonparametric statistics will be utilized in the analysis. Effect size of the three doses for all outcome measures for Stage 1, Stage 2, and 12 months after the final experimental session will be estimated using Cohen's techniques.

The Sponsor will examine each active dose group and the comparator dose group for homogeneity through comparing demographic characteristics. There is no expectation that conditions will differ in composition by gender, race or ethnicity, duration of PTSD diagnosis or presence versus absence of other permitted psychiatric disorders, as depression. However, owing to small sample size, such variations may arise by chance.

The Sponsor will examine CAPS scores for the primary outcome analysis at baseline and the primary endpoint in each active dose and comparator dose conditions. Active dose 1 and active dose 2 CAPS data at the primary endpoint will be tested for equivalence using confidence intervals. If the two groups are found to be equivalent, then outcomes for the active dose groups will be combined and will be tested for significant differences from the comparator group using difference scores in independent sample t-tests, with p value set at 0.05. If CAPS scores for active dose 1 are not equivalent to active dose 2, then analysis of variance (ANOVA) will be used to compare outcomes from all three groups. Additional exploratory analyses comparing the effect of a third experimental session with either active dose 1 or active dose 2 may be conducted if sufficient group sizes are attained, and analyses comparing outcomes at third session may be conducted with and without active dose 2 participants who elected to take active dose 1 during the third experimental session.

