12.1 Statistical Power

This is a pilot study intended to collect and compare estimates of effect size for each active dose and the comparator dose. The study is underpowered for detection of differences of a small or moderate effect size, and it may detect differences if the effect size is large.

Analyses of MAPS' completed U.S. study of MDMA-assisted psychotherapy in 20 people with PTSD found an effect size of 1.24 for treatment efficacy, as represented by changes in CAPS score [166]. The estimated effect size for this study may be lower as a result of comparing each active dose with the comparator dose instead of with an inactive placebo, small sample size, and unequal distribution of conditions. The sponsor intends to pool data across studies or perform meta-analyses of CAPS scores across all pilot studies.

The sponsor used Java applications created by Lenth to calculate estimated statistical power for the primary outcome measure of this study. The calculation assumed that active dose 1 and active dose 2 would be equivalent and could be combined, assuming an effect size of 0.8 for the impact of two sessions of MDMA-assisted psychotherapy on symptoms of PTSD [167], reducing the effect size to account for the hypothesized effects of using a comparator dose of 40 mg that is higher than the 25 mg dose employed as an active placebo in a sponsor-supported study. The software calculated an estimated power of 0.33 for a comparison of 18 versus 5, indicating an underpowered study. Had we used the higher effect size of 1.1, power analysis still indicates that this study is underpowered, with an estimated effect size of 0.55, but higher than previously calculated prior to the addition of these subjects. Statistical power estimates were not available for secondary and exploratory measures, as they were previously not used in sponsor-supported studies.

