7.0 Sample Size and Power Considerations

This study is a pilot investigation intended to gather preliminary data on the safety and efficacy of MDMA in 26 subjects with chronic, treatment-resistant PTSD. Because of their exploratory nature, pilot studies are often not powered for detecting the desired effect. Because it is a pilot study in a small sample, results will be used to collect effect size estimates for statistical power calculations for adequately powered subsequent studies.

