9.9.1 Primary Efficacy Analyses

Clinician Administered PTSD Scale-4 (CAPS-4)

The primary efficacy evaluation is the change from baseline to the primary outcome timepoint (visit 12) in the CAPS-4 Global Severity score of PTSD (difference score). The primary efficacy comparison will be made with ANOVA at an alpha level of 0.05. If the primary hypothesis rejects, pairwise comparisons among the treatment groups will be made with t-tests. If the parametric assumptions for the ANOVA and t-test analyses are not met, the analogous nonparametric methods will be used (Kruskall-Wallis, Wilcoxon Rank-Sum).

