9.9.3 Exploratory Analyses

Clinician Administered PTSD Scale-4 (CAPS-4)

- The percentage of subjects who achieve a 30% drop in CAPS-4 global score at the primary endpoint (visit 12) will be an indirect measure of clinical significance. Descriptive statistics will be computed and displayed by Stage 1 treatment groups.
- The percentage of subjects who no longer meet PTSD diagnostic criteria according to the CAPS-4 at the primary endpoint (visit 12) will be an indirect measure of clinical significance. Descriptive statistics will be computed and displayed by Stage 1 treatment groups.

- CAPS-4 Subscale Scores (B, C, D, F) at the primary endpoint (visit 12) will be analyzed in the same manner as the primary analysis of the global score. Descriptive statistics will be computed and displayed by Stage 1 treatment groups.
- Active dose 1 (125mg) and Active dose 2 (100mg) CAPS data at the primary endpoint will be tested for equivalence using confidence intervals. If the two groups are found to be equivalent, then outcomes for the active dose groups will be combined and will be tested for significant differences from the comparator group using difference scores in independent sample t-tests, with p value set at 0.05.
- Comparison of the effect of a third experimental session with either Active dose 1 or Active dose 2 may be conducted if sufficient group sizes are attained, and analyses comparing outcomes at third session may be conducted with and without Active dose 2 participants who elected to take Active dose 1 during the third experimental session.
- Two regression analyses will be conducted using (1) all subjects with a Frequency score of 2 or greater and an Intensity score of 2 or greater on the CAPS Associated Features 29 or 30 at baseline and (2) baseline DES-II total score as baseline covariates to determine whether the dissociative subtype of PTSD is predictive of treatment outcomes.

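### The only power figures in the plan (0.33 and 0.55, the second misprinted as an effect size) belong to a pooled 18-versus-5 t-test, not to the three-group ANOVA that the SAP makes primary

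*SAP*

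**What the plan says.** Protocol 12.1 gives the only power figures in either document. On its premise it says: "The calculation assumed that active dose 1 and active dose 2 would be equivalent and could be combined". At an effect size of 0.8: "The software calculated an estimated power of 0.33 for a comparison of 18 versus 5, indicating an underpowered study". At an effect size of 1.1 it says that "power analysis still indicates that this study is underpowered, with an estimated effect size of 0.55".

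Protocol 12.0 makes the primary comparison conditional on an equivalence check of the two active doses. One branch reads: "If the two groups are found to be equivalent, then outcomes for the active dose groups will be combined", followed by a t-test against the comparator on difference scores. The other reads: "If CAPS scores for active dose 1 are not equivalent to active dose 2, then analysis of variance (ANOVA) will be used", covering all three groups.

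SAP 9.9.1 has no such condition: "The primary efficacy comparison will be made with ANOVA at an alpha level of 0.05". Pairwise t-tests follow only if that test rejects. The equivalence step appears in SAP 9.9.3, among the exploratory analyses: "Active dose 1 (125mg) and Active dose 2 (100mg) CAPS data at the primary endpoint will be tested for equivalence using confidence intervals". SAP 7.0 gives no power for any test and remarks only that "pilot studies are often not powered for detecting the desired effect".

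The supplied protocol plans 23 subjects at 9:9:5 (5.3). The SAP follows Amendment 6, with 26 subjects at 12:9:5 (6.0).

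**The concern.** Two things look wrong. First, an effect size of 1.1 is assumed and the result is then reported as an effect size of 0.55, which makes no sense as printed. Second, a power figure describes one test. The SAP's primary test is not the one for which power was calculated, and the SAP supplies no replacement figure.

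What is at stake is how the result is read. The ANOVA is tested at 0.05 and controls access to the pairwise comparisons with 40 mg. Someone interpreting a non-significant ANOVA who takes 0.33 or 0.55 from the protocol is using the power of another test, with different degrees of freedom.

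**Working it through.** **Inputs.** Effect sizes d = 0.8 and 1.1, equal active doses, and 18 versus 5 (Protocol 12.1). Alpha 0.05 (SAP 9.9.1), two-sided tests (SAP 9.0). Allocation 9:9:5 (Protocol 5.3) and 12:9:5 (SAP 6.0). SD is set to 1 because d is standardised.

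**Step 1: reproduce the stated figures.** Two-sample t-test, df = 18 + 5 − 2 = 21, noncentrality d·√(18·5/23) = 1.978·d.
- d = 0.8: noncentrality 1.58, power 0.327 (stated 0.33).
- d = 1.1: noncentrality 2.18, power 0.546 (stated 0.55).

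A one-sided test would give 0.455 and 0.677, and a normal approximation 0.353 and 0.586; neither matches. The stated figures are therefore the two-sided pooled t-test, and 0.55 is a power.

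**Step 2: power of the SAP's primary test under the same assumption.** One-way ANOVA, three groups of 12, 9 and 5, means (d, d, 0), df = 2 and 23. Noncentrality λ = Σnᵢ(μᵢ − μ̄)² = d²·(21·5/26) = 4.038·d².
- d = 0.8: λ = 2.58, power 0.251.
- d = 1.1: λ = 4.89, power 0.441.

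**Step 3: pooled test on the same 26 subjects.** 21 versus 5, df = 24, noncentrality d·√(21·5/26) = 2.010·d. Power is 0.339 and 0.564. Its squared noncentrality equals λ in Step 2. The ANOVA loses power almost entirely because it spends a second numerator degree of freedom on a between-dose difference assumed to be zero.

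| Equal active doses | d = 0.8 | d = 1.1 |
|---|---|---|
| Pooled t, 18 v 5 (stated basis) | 0.327 | 0.546 |
| ANOVA 9:9:5 | 0.241 | 0.422 |
| Pooled t, 21 v 5 | 0.339 | 0.564 |
| ANOVA 12:9:5 | 0.251 | 0.441 |

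Same-subject gap at 12:9:5: 0.339 − 0.251 = 0.09, and 0.564 − 0.441 = 0.12. A simulation of 200,000 trials agreed (ANOVA 0.253 / 0.440; pooled 0.340 / 0.564).

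**Step 4: unequal doses, same subjects, both tests.** Means (d, f·d, 0) at 12:9:5, where f is the 100 mg effect as a fraction of the 125 mg effect. The documents give no value for f. ANOVA power is from the noncentral F; pooled-test power for f below 1 is simulated.

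| f | d = 0.8: ANOVA v pooled | d = 1.1: ANOVA v pooled |
|---|---|---|
| 0 | 0.38 v 0.12 | 0.65 v 0.16 |
| 0.25 | 0.29 v 0.16 | 0.51 v 0.26 |
| 0.5 | 0.24 v 0.22 | 0.42 v 0.36 |
| 0.6 | 0.23 v 0.24 | 0.40 v 0.40 |
| 1 | 0.25 v 0.34 | 0.44 v 0.56 |

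The two tests cross at f of about 0.55 to 0.6. Over f from 0 to 1 the ANOVA's power runs from 0.22 to 0.38 (d = 0.8) and from 0.39 to 0.65 (d = 1.1), with its minimum near f = 0.71.

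**The case against.** The strongest reply is that nobody is misled. Protocol 12.1 says openly that it pools the doses and compares 18 with 5, and it calls the study underpowered. SAP 7.0 says much the same of pilots in general. This largely stands and is why the point is minor. It does not rescue the 0.55 label, and it does not supply a power for the ANOVA.

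Second, the supplied protocol predates the SAP's sample size. Amendment 6 may have revised 12.0 and 12.1. That cannot be seen, so the mismatch between the documents is established only for the supplied text. What the SAP itself reports of Amendment 6 (6.0 and 9.3) concerns enrolment. Whatever the amendment says, SAP 7.0 still gives no power.

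A reader might infer that the ANOVA is simply the weaker choice and that the SAP gave up power by adopting it. The documents do not support that. The loss follows from the equal-dose assumption. The pooled test also loses power when the doses differ, so a fair comparison must put both tests on the same subjects and the same effects. On that basis (Step 4) the ANOVA is ahead until the 100 mg effect reaches a little over half of the 125 mg effect.

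A reader might also infer that the protocol must be changed to match the SAP. That does not follow either. SAP 2.0 describes its plan as derived from the protocol's, and SAP 5.0 gives the protocol the final word, so the direction is open.

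**Conclusion.** Minor, but wrong as written. Two conclusions hold:

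- The protocol's 0.55 is a power mislabelled as an effect size. This is firm and does not depend on Amendment 6.
- On the supplied text, no stated power applies to the SAP's primary test. If both active doses work equally, that test has power of about 0.25 (d = 0.8) and 0.44 (d = 1.1), which is 0.09 and 0.12 below the pooled test on the same subjects.

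The ANOVA figures assume normal data and all 26 subjects analysed at 12:9:5. They do not cover the rank-based fallback in SAP 9.9.1 or a 100 mg effect larger than the 125 mg effect. SAP 9.9.1 names no analysis population, and the arms of the subjects mentioned in SAP 9.3 are not given. With equal doses, adding the two replaced withdrawals to the 26 (an assumption) gives 0.26 / 0.45 to 0.32 / 0.56, depending on their arms. Removing the three subjects with exclusionary conditions from the 26 (also an assumption) gives 0.24 / 0.42, falling to 0.13 / 0.22 if all three were on 40 mg.

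No sample-size decision changes. Confidence is high for the arithmetic and the label, and medium for the mismatch between the documents.

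**What to change.** 1. Protocol 12.1: relabel 0.55 as an estimated power, and add that 0.33 (effect size 0.8) and 0.55 (effect size 1.1) apply only to the t-test of the pooled active doses (n = 18) against the comparator (n = 5).
2. SAP 7.0, and Protocol 12.1 if the ANOVA is primary there too: add: *Power of the three-group ANOVA (alpha 0.05; 12, 9 and 5 subjects analysed) is about 0.25 (d = 0.8) and 0.44 (d = 1.1) if both active doses have the same effect versus 40 mg.* Optionally add the ranges 0.22-0.38 and 0.39-0.65 for a 100 mg effect between zero and the 125 mg effect. Name the analysis population to which the arm sizes refer.
3. Unless Amendment 6 already did so, reconcile Protocol 12.0 and SAP 9.9.1 before any unblinded analysis so that both name the same primary test, in whichever direction the sponsor chooses, and quote the power of that test. The equivalence analysis in SAP 9.9.3 can remain exploratory if the ANOVA is kept.

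Items 1 and 2 are wording only; item 3 may need an amendment. No data or sample size changes. The price is a less favourable power figure if the ANOVA is kept.

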9.9.2 Secondary Efficacy Analyses

The secondary efficacy analyses will be made with ANOVA comparing change from baseline (Baseline) to the primary outcome timepoint (visit 12) of all the secondary measures, following the same methodology used for the primary endpoint. If the parametric assumptions for the ANOVA analyses are not met, the analogous nonparametric methods will be used (Kruskall-Wallis, Wilcoxon Rank-Sum).

PTSD Diagnostic Scale (PDS) total score will be analyzed in the same manner as the CAPS-4 global scale primary analysis.

Global Assessment of Functioning (GAF) total score will be analyzed in the same manner as the CAPS-4 global scale primary analysis.

Beck Depression Inventory-II (BDI-II) total score will be analyzed in the same manner as the CAPS-4 global scale primary analysis.

Post Traumatic Growth Inventory (PTGI) total will be analyzed in the same manner as the CAPS-4 global scale primary analysis.

Dissociative Experiences Scale-II (DES-II) total will be analyzed in the same manner as the CAPS-4 global scale primary analysis.

Pittsburgh Sleep Quality Index (PSQI) global scores will be analyzed in the same manner as the CAPS-4 global scale primary analysis.

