subjects will complete the PTGI in reference to the time since the trauma at baseline, but will respond in reference to the beginning of their participation in the study on all subsequent occasions. Subjects will complete the PTGI according to the Time and Events table.

The DES-II is a 28-item self-report measure of dissociation, defined as a lack of normal integration of an individual's thoughts, feelings, or experiences into the stream of consciousness or memory [127, 128]. It is an established measure of dissociative symptoms. The scale consists of statements describing facets of dissociation. Respondents indicate how often the specific experience happens to them, from "never" to "always." Responses on the original scale were made via visual analog scales. The DES-II uses the same items but with responses made on a ten-point scale from "0%" to "100%" of the time. The scale is scored by treating percentages as single digits to produce a total score. The DES-II can also be used to produce scores for three factors, amnesia, depersonalization, and derealization. The scale differentiated between respondents without psychiatric disorders or with psychiatric disorders with few dissociative symptoms and respondents with psychiatric disorders associated with dissociative symptoms [127]. Reliability of the DES-II is high (ranging from 0.79 to 0.96 in an early review), and a reported Cronbach's alpha of 0.95 [128, 129]. There may be a relationship between experiencing dissociation and occurrence of chronic PTSD [128, 130].

The long-term follow-up questionnaire has been developed internally by the Sponsor to assess long-term benefits and harms of MDMA-assisted psychotherapy at the long-term follow-up visit.

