- Last-month CAPS to assess PTSD symptoms and eligibility, which may be recorded to video in as many instances as necessary to establish inter-rater reliability.
- GAF to assess general psychological function.
- PASAT to assess cognitive function.
- RBANS to assess cognitive function.

The subject will complete the following self-report measures:

- PTGI (in reference to time since the trauma)
- PDS to assess self-reported PTSD symptoms
- BDI-II to assess depression symptoms
- PSQI to assess sleep quality

- DES-II to assess dissociation symptoms

5.2.2 Preparatory Psychotherapy Sessions - Visits 1, 2, 3 (Stage 1), 18 (Stage 2)

Subjects who do not complete all screening activities will not be enrolled. Eligibility may be discussed by phone after screening is complete and at the time Visit 1 is scheduled but the final confirmation will occur at Visit 1. If all inclusion criteria and no exclusion criteria are met, eligibility will be confirmed with the subject.

- a. Complete a final review of Inclusion/exclusion criteria.
- b. Assess general wellbeing.
- c. Confirm eligibility and willingness to participate in study.
- d. Enroll subject and issue subject number.
- e. Ensure medical history and medication history is complete. After enrollment new events will be collected as AEs and new medications, as described in Sections 8.5 and 9.0.
- f. Discuss medication tapering, if applicable. Upon confirmation of eligibility, the study physician will consult the prescribing physician to initiate medication tapering for subjects who must refrain from taking a psychiatric medication for the study. Tapering will follow a time course appropriate for the medication given its half-life, with the first experimental session scheduled to occur after complete washout. Individuals using opiates for pain management will be asked to decrease the dose or avoid taking their pain medication for 24 hours prior to experimental sessions if possible, as these medications may reduce the efficacy of MDMA. Subjects will be permitted to take their prescribed opiate medication during this period if necessitated by pain flare-ups.

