5.2.7 Evaluation at Primary Endpoint and Unblinding - Visit 12 (Stage 1)

The primary endpoint evaluation in Stage 1 will occur one month (within a window of plus or minus two weeks) after the second blinded experimental session. This visit will consist of two meetings that may be completed on separate days, one with the IR and the other with the therapists. Subjects who have withdrawn from treatment but have continued for follow-up will also complete this time point one month after their last experimental session.

At the primary endpoint:

- a. Subjects will meet the IR for at least an hour and a half.
- b. The blinded IR will administer:
 - Last month CAPS to assess PTSD symptoms, which may be recorded to video in as many instances as necessary to establish inter-rater reliability.
 - GAF to assess general psychological function.
 - PASAT to assess cognitive function.
 - RBANS to assess cognitive function.
- c. The subject will complete the following self-report measures:
 - PTGI to assess post-traumatic growth (in reference to start of the study)

- PDS to assess PTSD symptoms.
 - BDI-II to assess depression symptoms.
 - PSQI to assess changes in sleep quality.
 - DES-II to assess dissociation symptoms.
- d. After completing all assessments and measures with the IR, the subject will meet with the therapists for approximately 30 minutes.
 - e. The therapists will assess suicidality with the C-SSRS.
 - f. General wellbeing will be assessed.
 - g. The visual analog scale will be used to collect changes in pre-existing tinnitus and chronic pain symptoms.
 - h. The blind will be broken for the subject's condition assignment. Only the IR will remain blind to condition assignment at this time.
 - i. If the subject was assigned to receive comparator dose MDMA, the therapists will discuss enrollment in Stage 2 (see Section 5.2.9). Comparator dose subjects will not complete the third experimental session and associated integrative sessions in Stage 1.
 - j. Collect perceptions of experimental sessions from active dose subjects after unblinding.
 - k. If the subject was assigned to receive active dose MDMA, the subject will complete a third open-label experimental session, with associated daily phone calls and integrative sessions in Stage 1 (see Sections 5.2.3-6).

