The sponsor will collect Changes in Tinnitus and/or Pain visual analog scale scores from any subject reporting tinnitus or chronic pain during each point of administration, including baseline, experimental and integrative sessions, the primary endpoint, and two-month follow-up. The sponsor will plot out and examine all changes in tinnitus and/or pain visual analog scale scores across both groups and in each active dose group and the comparator dose group for trends. Formal analysis of changes in tinnitus and/or pain visual analog scale scores will only occur if three or more subjects complete changes in tinnitus and/or pain visual analog scale at baseline and primary endpoint. Likewise, formal between-groups analyses will not be performed if all primary endpoint scores are from subjects assigned to the same condition. The sponsor will perform an independent t-test on the difference between baseline and primary endpoint Changes in Tinnitus and/or Pain visual analog scale scores between each active dose and comparator dose conditions, with p. set at 0.05. If the only scores available are for subjects in a single condition, then a paired t-test will be performed comparing baseline and primary endpoint Changes in Tinnitus and/or Pain visual analog scale scores, with p. set at 0.05.

Perception of the experimental sessions will be examined during Stage 1 and Stage 2, before and after subjects have undergone a third experimental session. The results of this exploratory analysis will inform the sponsor of expectancies and the value of the third session for future protocol development. These data may be correlated with primary/secondary endpoint CAPS data compared to end of Stage 1/Stage 2 CAPS data to assess the potential contribution of expectation and self-reported response to changes in PTSD symptoms.

The sponsor will compare CAPS, PDS, PTGI, GAF, BDI-II, PSQI, and DES-II, scores at the final two-month follow-up assessment to the 12-month follow-up using difference scores in an independent t-test for a within-subject analysis with p value set at 0.05.

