4.2 Secondary Objectives

The following objectives will compare each active dose group and the comparator dose group in Stage 1:

- Assess changes in self-reported PTSD symptoms as measured with the PTSD Diagnostic Scale (PDS) at baseline, after each experimental session and/or the primary endpoint.
- Assess depression symptoms with the Beck Depression Inventory-II (BDI-II) at baseline and the primary endpoint.
- Assess global functioning with the Global Assessment of Functionality (GAF) at baseline and the primary endpoint.
- Assess self-reported sleep quality with the Pittsburgh Sleep Quality Index (PSQI) at baseline and the primary endpoint.
- Assess self-reported dissociation symptoms with the Dissociative Experiences Scale II (DES-II) at baseline and the primary endpoint.
- Assess self-reported posttraumatic growth with the Posttraumatic Growth Inventory (PTGI) at baseline and the primary endpoint.

The following objectives will compare effects in specified subjects:

- Assess PTSD symptoms via CAPS and PDS, depression symptoms via BDI-II, global functioning via GAF, sleep quality via PSQI, posttraumatic growth via PTGI, and dissociation symptoms via the DES-II, throughout Stage 2 in comparison to Stage 1 in crossover subjects.
- Assess long-term effects of MDMA-assisted psychotherapy on symptoms of PTSD, depression, and global function, sleep quality, dissociation symptoms via CAPS and PDS, BDI-II, GAF, PSQI, PTGI (in reference to start of the study), and DES-II one year after the final experimental session for each subject.

The following objectives will include exploratory analyses intended to inform future protocol design:

- Explore the effects of each experimental session upon self-reported changes in consciousness, as those associated with a transformational or mystical experience via the States of Consciousness Questionnaire (SOCQ).
- Assess the effect of the third experimental session for active dose subjects in Stage 1 and Stage 2 using CAPS, PDS, BDI-II, GAF, PSQI, PTGI (in reference to start of the study), and DES-II.
- Assess the ability of the investigators and subjects to accurately guess treatment group assignment in Stage 1.
- Correlate adherence to the treatment manual with Global CAPS scores using adherence criteria ratings to assess videos of psychotherapy sessions.

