9.5 Baseline Values

Baseline values are from screening/baseline visit for all measures, except C-SSRS. For C-SSRS, pre-enrollment scores will be used as a measure of ‘lifetime’ suicidal ideation and behavior, and preparatory session 2 (visit 2) prior to drug administration will be used as ‘baseline.’ If a subject was not administered the C-SSRS at preparatory session 2 (visit 3), then ‘baseline’ scores will be visit 4 pre-drug C-SSRS observation.

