9.9.2.1 Secondary Efficacy Analyses at Secondary Endpoints

Assess 3 vs. 2 experimental MDMA sessions

For the CAPS, the absolute changes in the measure from the primary endpoint to end of Stage 1 for the 100 and 125 mg groups will be compared with t-tests. In the crossover subjects (40 mg) the absolute changes in the measures from the secondary (visit 27) endpoint to end of Stage 2 (visit 32) will be compared with t-tests.

Crossover Subject Analyses

CAPS data from subjects assigned to the 40 mg group in Stage 1, i.e. ‘crossover population,’ will be analyzed by t-tests on difference scores from primary endpoint (visit 12) in Stage 1 to secondary endpoint in Stage 2 (visit 27). Additionally, the following measures’ total scores will be analyzed in this same fashion: CAPS, PTGI, BDI-II, GAF, PSQI, DES-II, PDS.

Long-term Follow-up

For the CAPS, PDS, PTGI, BDI-II, GAF, PSQI, and DES-II, the absolute changes in the measures from baseline to the long-term follow-up visit (one year post final experimental year) will be compared with t-tests. The absolute changes in the measures from long-term follow-up to End of Stage 1 (visit 17, 100 mg and 125 mg) or long-term follow-up compared to End of Stage 2 (visit 32, 40 mg) will be compared with t-tests.

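### PTGI change from baseline subtracts a rating of growth since the trauma from a rating of growth since study start, so it is not change in one quantity

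*SAP*

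**What the plan says.** **Administration.** Protocol 5.1.1 has subjects complete the PTGI at baseline with reference to the time since the trauma, "but will respond in reference to the beginning of their participation in the study on all subsequent occasions". The visit procedures repeat this. Screening (Protocol 5.2.1) lists "PTGI (in reference to time since the trauma"), and visit 12 (Protocol 5.2.7) lists "PTGI to assess post-traumatic growth (in reference to start of the study"). The 12-month visit (Protocol 5.2.10) also uses study start. The SAP's own long-term objective (4.2) keeps that reference: "PTGI (in reference to start of the study), and DES-II one year after the final experimental session for each subject".

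**Analysis.** SAP 9.5 states "Baseline values are from screening/baseline visit for all measures, except C-SSRS". SAP 9.9.2 then analyses change from that baseline to visit 12: "Post Traumatic Growth Inventory (PTGI) total will be analyzed in the same manner as the CAPS-4 global scale primary analysis". SAP 9.9.2.1 adds a t-test comparison of "For the CAPS, PDS, PTGI, BDI-II, GAF, PSQI, and DES-II, the absolute changes in the measures from baseline to the long-term follow-up visit". None of these makes an exception for the PTGI. Protocol 12.0 also plans an ANOVA on PTGI change between dose conditions.

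**PDS (separate, minor).** The exploratory repeated-measures ANOVA in SAP 9.9.3 uses baseline, the PDS after the sessions at visits 4 and 13, and visit 17, with Stage 1 group as the between-subjects factor.

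**The concern.** A change score needs the same quantity measured twice. Here the visit 12 rating is already a report of growth over the study. Subtracting a report of growth over another period, one that starts at the trauma, leaves a number with no meaning as change.

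Posttraumatic growth is a listed secondary objective. If the plan is followed as written, the report may show a PTGI gain or decline within an arm, and may call it significant at follow-up, when all that differs is the period subjects were asked about.

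**Working it through.** **1. Reference point of each planned PTGI contrast.**

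| Contrast | Earlier rating | Later rating | Same starting point? |
|---|---|---|---|
| Baseline to visit 12 (SAP 9.9.2; Protocol 12.0) | trauma | study start | No |
| Baseline to long-term follow-up (SAP 9.9.2.1) | trauma | study start | No |
| Visit 12 to visit 27, crossover (SAP 9.9.2.1) | study start | study start | Yes |
| Visit 17 or 32 to long-term follow-up (SAP 9.9.2.1) | study start | study start | Yes |

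Only the contrasts that use the screening value fail.

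**2. Within-arm change depends on the mismatched baseline.** The documents give no PTGI mean, SD or correlation, so these means are assumed. Hold the visit 12 means at 50 (125 mg) and 30 (40 mg), and move only the since-trauma mean:

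| Baseline mean | 125 mg change | 40 mg change | Difference between arms |
|---|---|---|---|
| 20 | 50 − 20 = +30 | 30 − 20 = +10 | 20 |
| 40 | 50 − 40 = +10 | 30 − 40 = −10 | 20 |
| 60 | 50 − 60 = −10 | 30 − 60 = −30 | 20 |

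The within-arm figure changes size and sign while the visit 12 ratings stay fixed. The randomised contrast does not move.

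**3. A within-subject baseline-to-follow-up test, if one is run.** Suppose the reference period alone shifts scores by a given number of SDs. With equal SDs at both times, the standardised paired difference is shift/√(2(1−ρ)). Noncentral-t probabilities of p ≤ 0.05 (two-sided) at ρ = 0, 0.5 and 0.8, for the planned arm sizes:

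| n | 0.5 SD shift | 1 SD shift |
|---|---|---|
| 5 | 0.10, 0.14, 0.28 | 0.23, 0.40, 0.75 |
| 9 | 0.16, 0.26, 0.55 | 0.46, 0.75, 0.985 |
| 12 | 0.20, 0.35, 0.70 | 0.61, 0.88, above 0.99 |

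These show what such a shift could do. They do not estimate it.

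**4. Between-arm ANOVA at visit 12.** With equal SDs σ, Var(change) = 2σ²(1−ρ) and the ANCOVA residual variance is σ²(1−ρ²). The ratio is 2(1−ρ)/(1−ρ²) = 2/(1+ρ), which is 2.00, 1.33 and 1.11 at ρ = 0, 0.5 and 0.8.

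In simulated 12/9/5 trials with a common 1 SD shift and no arm effect, type I error of the ANOVA on change is 0.048, 0.050 and 0.050. With assumed effects of 0.8, 0.8 and 0 SD, its power is 0.14, 0.25 and 0.56, against 0.24, 0.31 and 0.58 for ANCOVA. Unadjusted visit 12 totals give 0.25 throughout.

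**5. PDS.** The schedule takes the PDS at the third integrative session (visits 7 and 16), and visits 13 to 17 are for active-dose subjects only. Of the four SAP time points, the 40 mg arm can fill two (baseline and visit 7), so 10 of 12 group-by-time cells are observable. The PDS after session 2, taken at visit 12 (Protocol 5.2.6), is omitted, although Protocol 12.0 asks for PDS after every session.

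**The case against.** The case for leaving the plan alone has real substance:

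- **The planned visit 12 test is a randomised comparison.** This stands. A reader might infer that the between-arm ANOVA is biased by the mismatch. It is not: a shift common to all arms cancels, as steps 2 and 4 show.
- **SAP 9.9.2.1 does not say that its t-tests are paired.** This stands. Protocol 12.0 does not settle it either, because it compares "scores at the final two-month follow-up assessment to the 12-month follow-up using difference scores in an independent t-test for a within-subject analysis", which names two designs at once. That comparison also runs between two post-baseline visits. Step 3 is therefore conditional.
- **The weight is limited.** This is a pilot for estimating effect sizes, and Protocol 12.0 introduces the PTGI as exploratory. SAP 9.9 restricts effect sizes to measures of interest without naming the PTGI, although Protocol 12.0 asks for them on all outcome measures.
- **The protocol also plans PTGI change.** True, but that repeats the problem at visit 12. The baseline-to-follow-up comparison appears only in the SAP.
- **Versions differ.** The supplied protocol is for 23 subjects, while the SAP follows Amendment 6 with 26 and does not restate the baseline reference. SAP 5.0 does name the protocol as definitive, so this is a caveat and not a rebuttal.

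A reader might also infer a direction: a shorter look-back after baseline, hence a spurious decline. The documents do not support this. PTSD of at least six months puts the trauma at least that far back. Visit 12 falls about 10 to 14 weeks after enrolment (3–5 + 3–5 + 4.35), or up to about 22 weeks if participation is counted from screening (13 + 5 + 4.35). By the 12-month visit the look-back is about 15 to 18 months (Protocol 4.1), which can exceed the baseline minimum. The defect is a different starting point, not a shorter period.

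**Conclusion.** The point holds for every PTGI quantity that contrasts the screening value with a later one within subjects or within arms: descriptive change, each arm's pre-post term in a PTGI effect size, and a baseline-to-follow-up within-subject test if run. None can be read as change, and their size and sign cannot be predicted from the documents.

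It does not invalidate the between-arm test at visit 12. There the cost is precision: error variance 2/(1+ρ) times that of ANCOVA, assuming equal SDs, with ρ not given. Contrasts between post-baseline visits are sound.

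The conclusion about meaning rests on the documents' own wording and needs no assumed figure. The probabilities in step 3 and the power figures in step 4 rest wholly on assumed shifts, effects and correlations. The sponsor should make the change, since it concerns a listed secondary objective and costs little.

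The PDS point is separate, minor and exploratory. A complete-case fit would keep none of the five planned comparator subjects, but the SAP does not specify such a fit, and SAP 9.3 speaks of using all available data. The empty cells and the missing session 2 remain in either case. The secondary PDS analysis from baseline to visit 12 is unaffected.

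**What to change.** **PTGI**

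- In SAP 9.9.2, compare visit 12 PTGI totals between groups, with the since-trauma baseline rating as a covariate.
- Report no baseline-to-post PTGI change, no pre-post PTGI effect size and no within-subject test against baseline.
- At long-term follow-up, report PTGI totals descriptively. A between-arm ANCOVA there is not a good substitute: 40 mg subjects may by then have had Stage 2 active doses, and planned durations of 15 against 18 months give the arms different look-backs.
- Keep the contrasts between post-baseline visits: visit 12 to visit 27, and follow-up against visit 17 or 32. They share the study-start reference, and the follow-up contrast matches the 12-month comparison in Protocol 12.0.
- State in SAP 9.5 that the PTGI baseline has a different reference, and document the departure from Protocol 12.0, which plans ANOVA on PTGI change.

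**PDS (minor).** Fit the three-arm model on baseline, visit 7 and visit 12. Analyse visits 16 and 17 in the active-dose groups only.

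**Cost.** No new data are needed. The price is a small documented departure from the protocol and the loss of a PTGI change-from-baseline figure. If the baseline correlation is near zero, the covariate gains nothing over unadjusted visit 12 totals (power 0.24 against 0.25 under the assumptions above), but the comparison remains interpretable.
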